14.9 Cohort Analyses and Monitoring

As described in [Section 4.2.1](#), the decision to escalate doses from cohort to cohort will only occur based on consensus supporting escalation by PI (or designee) and the medical monitor. The medical monitor and the PI (or designee) will review aggregate safety data up through Day 14 from all dosed participants from the prior dose cohort.

An independent Safety Monitoring Committee (SMC) will receive monthly study progress and safety monitoring reports. Study feasibility and the achievement of study milestones will be assessed in these reports. Additionally, accrual, baseline characteristics, conduct of the study (including premature study discontinuations), any interruptions of ART, virologic failures, and all reported toxicities and events will be monitored during the study on a monthly basis. The

individual safety data will be reviewed monthly to assess relation of all reported toxicities and AEs to the study treatment. The monthly data will be shared with the SMC for review.

If at any time during the study, two or more participants experience a toxicity that is Grade 3 or higher and definitely, probably, or possibly related to study treatment (as judged by the protocol team), or two or more participants experience the same DLT that is Grade 2 or higher, then enrollment into the study will be temporarily suspended and the independent SMC will be asked to review all safety data; review the relation to study treatment of the event(s); and recommend how the study should proceed with respect to resuming enrollment and continuing study treatment.

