4.4 Dose Limiting Toxicity

DLT will be defined based on drug-related AEs that occur during the DLT period following MGD014 administration. For Part 1, the DLT period is 2 weeks following the single MGD014 infusion. For Part 2, the DLT period is defined as the period from initial infusion of MGD014 through 2 weeks following the last IV MGD014 infusion.

The severity of all AEs will be graded according to the Division of AIDS Table for Grading the Severity of Adult and Pediatric Adverse Events, corrected Version 2.1, July 2017, which can be found on the DAIDS Regulatory Support Center Web site: <http://rsc.tech-res.com/clinical-research-sites/safety-reporting/daids-grading-tables>.

A DLT is any \geq Grade 2 drug-related AE, with the following exceptions, based on the medical judgement of PI (or designee) and medical monitor:

- Grade 2 laboratory abnormality that lasts <72 hours and is not otherwise associated with clinical complications.
- Grade 2 fatigue that lasts <7 days.

In general, for participants who experience an AE that meets criteria for a DLT, subsequent administration of the study drug to that participant should be held pending management and/or resolution of the event and assessment of attribution to the study drug.

In Part 1, if a given dose level is found to exceed the MTD, meaning that \geq 2 participants experience a DLT in a single dose cohort, Part 2 will proceed with the MTD (the dose preceding the dose level at which MTD was exceeded). If only 1 participant was enrolled at the prior dose level, an additional 3 participants will be enrolled at the prior dose level for evaluation of the MTD.

In Part 2, if \geq 2 participants experience the same DLT, subsequent administration of the study drug to any participant should be held pending review by the PI (or designee), sponsor, and independent Safety Monitoring Committee (SMC). If toxicity is unacceptable, the study will be discontinued.

All participants who discontinue study treatment or follow-up procedures should comply with end of study procedures. The sponsor or its designee must be notified about discontinuation within 24 hours of such an event.

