5.3 Guidelines for Discontinuation of Participants from Study Drug Administration

Under certain circumstances, an individual participant's infusions will be prematurely or permanently discontinued. Specific events that will result in stopping a participant's infusion schedule in either Part 1 or Part 2 of the study include:

- Failure to meet requirements established for safety assessment
- Pregnancy
- Development of a DLT at any time following MGD014 infusion
- Investigator discretion
- HIV RNA > 150 copies/mL on 2 consecutive determinations

If the PI (or designee) decides that a participant should be withdrawn from study treatment, the sponsor must be alerted within 24 hours. All participants who discontinue treatments should comply with protocol specified visits and follow-up as required by the protocol. The only exception to this requirement is when a participant withdraws consent for all study procedures or loses the ability to consent freely (i.e., is imprisoned or involuntarily incarcerated for the treatment of either a psychiatric or physical illness).

If a participant is withdrawn before completing the study, the reason for withdrawal must be documented appropriately in the study documents.

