6.5.2 Vehicle

6.6 Study Drug Preparation and Administration

6.6.1 General Guidelines and Precautions

MGD014 is administered to participants at very low doses. All doses employed in this study are described in units of micrograms/kilogram: A microgram (μg) is 1 millionth ($1/10^6$) of a gram (g), 1 thousandth ($1/10^3$) of a milligram (mg).

MGD014 is a CD3-targeting therapy. Therefore, it is possible that MGD014 may induce severe/fatal CRS when administered to humans. Errors in dilution could result in severe/fatal CRS.

Every reasonable precaution should be exercised in the preparation, verification, and administration of the MGD014 dose. Independent verification of participant weight, the calculated dose, and the IV pump setting must be reviewed and documented by a second individual trained in these procedures before study drug administration commences.

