12.2.6 Reporting of Adverse Events to the Sponsor and DAIDS

Throughout the study, the Investigator must document all AEs in the source documents (and database) in a timely manner. IREs, as defined in [Section 12.2.2](#) are events that must be reported immediately to MacroGenics Product Safety or designee within 24 hours of being identified and be entered into the database within 5 calendar days. The sponsor, MacroGenics, is responsible for reporting to DAIDS.

All reportable AEs must have their severity graded along with attribution to study drug recorded.

AEs leading to discontinuation, potential autoimmune events, AEs of \geq Grade 3 severity related to MGD014, as well as safety concerns will be communicated within 24 hours to MacroGenics and the UNC IRB, as required. MacroGenics will report to the DAIDS and FDA per their reporting requirements.

All AEs and SAEs must be followed until resolution, or they become chronic, or stable. The resolution status of such an event must be documented. In addition, the PI should report all follow-up for reportable AEs and SAEs to the UNC IRB and MacroGenics. MacroGenics will report all follow up to DAIDS and FDA.

The PI (or designee) will immediately complete and transmit the *Immediately Reportable Event (IRE)* Report Form, within 24 hours of identifying the event, to MacroGenics Product Safety or designee. The IRE Report Form and Completion Guidelines, and Contact Information for Reporting IREs, are found in the Study Procedures Manual.

For reports of pregnancy, the IRE Report Form AND the MacroGenics Pregnancy Exposure Form must be completed and transmitted. The Investigator must attempt to follow the pregnancy to term or termination in order to report the outcome and health status of the mother and child. The Pregnancy Exposure Form is found in the Study Procedures Manual.

Please refer to the [Table 2](#) for reporting timeframes by event type:

Table 2 Safety Reporting by UNC by Event Type

Event Type	Report to MG via Immediately Reportable Event Form within 24 hours of awareness	Pregnancy Exposure Form (within 24 hours of awareness) to MG	Adverse Event Form (UNC database)	Report to UNC IRB
All SAEs	X		X	X
Pregnancy in a study participant or partner of a study participant	X	X	X	X
AESIs: ≥ Grade 2 Cytokine Release Syndrome/Infusion-Related Reaction	X		X	X

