16.11 Discontinuation of the Study or Study Site

16.11.1 Discontinuation of Study Site

Site participation may be discontinued if MacroGenics, Inc., the Investigator, a regulatory authority, or the IRB/IEC of the study site deems it necessary for any reason.

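### In Part 2, with no earlier qualifying event in another participant, a first related Grade 4 or 5 event triggers neither ad hoc SMC review nor a defined hold on the others' infusions

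*Protocol*

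**What the plan says.** Protocol 14.9 gives the SMC two sources of information. The routine one is monthly: "The monthly data will be shared with the SMC for review". The ad hoc one needs two people. It applies at any time in the study if "two or more participants experience a toxicity that is Grade 3 or higher and definitely, probably, or possibly related to study treatment", or if two or more have the same DLT at Grade 2 or above. The consequence is that "then enrollment into the study will be temporarily suspended and the independent SMC will be asked to review all safety data". The SMC is then asked to advise on enrollment and on continuing treatment.

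Protocol 4.4 has a separate rule for Part 2. If two or more "participants experience the same DLT, subsequent administration of the study drug to any participant should be held pending review by the PI", the sponsor and the SMC. After one DLT, 4.4 holds only the participant who had it, and 5.3 requires that participant's infusions to stop.

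The reporting duties are prompt. Under 12.2.2 and 12.2.3 every serious adverse event goes to the sponsor within 24 hours. Under 12.2.6 related events of Grade 3 or higher, "as well as safety concerns will be communicated within 24 hours to MacroGenics and the UNC IRB, as required"; the sponsor then reports to DAIDS and FDA. None of these sections names the SMC as a recipient.

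The worst case is foreseen. Section 6.6.1 says that "it is possible that MGD014 may induce severe/fatal CRS when administered to humans". The SAP contains no stopping or SMC rule.

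**The concern.** Part 2 is the first repeat dosing of a first-in-human T-cell-redirecting agent, in up to 6 people, at 300 mcg/kg, the highest dose of Part 1. If one of them has a related life-threatening event or dies, the rules settle what happens to that person and who is told. They do not say what happens to the others' next infusions. The committee set up to advise on continuing treatment is not asked until a second participant is affected or the monthly report arrives.

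Part 1 is stricter. Under 4.2.1, Scenario 3, a single DLT, which may be only Grade 2, means that one additional participant is watched for the full 2 weeks before anyone else is dosed at that level. Part 2 has no equivalent after a first event of any grade.

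**Working it through.** The plan gives no operating characteristics for these rules, so there is no figure to reproduce. The check has two steps: apply the rules to possible event patterns, then find the schedule limit.

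**Step 1. What each rule does.** Inputs are 14.9 and 4.4. The 14.9 count runs across the whole study. The DLT rule in 4.4 is read as counting Part 2 participants.

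| Pattern | 14.9: SMC asked | 14.9: enrollment suspended | 4.4: all infusions held |
|---|---|---|---|
| One related Grade 4 or 5 event in Part 2, no earlier qualifying event in anyone else | No | No | No |
| As above, but another participant earlier had a different related Grade 3+ toxicity (Part 1 or 2) | Yes | Yes | No |
| As above, but another Part 2 participant earlier had the same DLT at Grade 2 | Yes | Yes | Yes |
| Two Part 2 participants with different related Grade 4 DLTs | Yes | Yes | No |
| Two Part 2 participants with the same DLT | Yes | Yes | Yes |

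The first row is the main gap. The second and fourth rows show another: 14.9 is met, yet the only thing it suspends is enrollment. Once all planned Part 2 participants are enrolled, that suspension changes nothing for those still being dosed.

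**Step 2. Infusions that could fall due before the SMC sees the event.** Inputs:
- Three infusions, on Days 0, 14 and 28 (2.4.4, Appendix 1).
- Monthly reports (14.9), taken as M = 30 days apart. This is an assumption; 28 and 31 were also tried.

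Put the event at t = 0, just after a report, with the next report at t = M. Another participant had infusion 1 at time s, with s ≤ 0. The remaining infusions fall at s + 14 and s + 28. Count those with 0 < t ≤ M.

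| First infusion of the other participant | s + 14 | s + 28 | Due before the report |
|---|---|---|---|
| −14 < s ≤ 0 | in (0, 14] | in (14, 28] | 2 |
| −28 < s ≤ −14 | already given | in (0, 14] | 1 |
| s ≤ −28 | already given | already given | 0 |

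The result is the same for M = 28, 30 and 31. It cannot exceed 3 − 1 = 2, because only two infusions remain after the first, so a longer reporting lag does not raise it. If the next report is 14 days away or less, at most 1 can fall due on nominal days, since the two are 14 days apart. The minimum is 0.

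**The case against.** The case on the other side has real substance.

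- **Much of the safety response is mandatory.** The 5.3 stop for the affected participant and the 24-hour reports are not optional. A reader might infer that everything after a first event is discretionary, or that no independent body hears of it for a month. The text supports neither: the IRB is told within 24 hours. Only the decision about the *other* participants is discretionary.
- **Several parties can act.** Section 5.3 lists "Investigator discretion" as a ground for stopping a participant's infusions. Section 5.4 allows withdrawal at the discretion of the IRB, FDA, the investigator and others. Under 16.11.1 the only site can be closed if the sponsor, the investigator, "a regulatory authority, or the IRB/IEC of the study site deems it necessary for any reason", and 16.11.2 lets the sponsor or a regulator end the study. Nothing forbids an early call to the SMC. These powers stand, but none is tied to a stated event and none is a defined pause.
- **The gap is conditional.** One earlier related Grade 3+ toxicity in another participant, even in Part 1, would make the first Part 2 event a 14.9 trigger. The documents say only that no infusion reaction or cytokine release syndrome was seen through Cohort 8 (2.4.3). They do not give the count of related Grade 3+ events.
- **The risk is thought low and the DLT bar is strict.** Sections 2.2.1 and 2.3 call the risk of cytokine release very low or extremely low, and almost any related Grade 2 event is a DLT. That lowers the chance of needing the rule. It does not supply one.
- **A charter or SOP may cover this.** It could not be checked, and neither 14.9 nor 4.4 refers to one.

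A reader might also multiply the per-person limit over the cohort, or count three infusions for someone who starts after the event. The documents give no Part 2 accrual overlap, so a cohort total has no basis. Three infusions within 30 days would need a first infusion no more than 30 − 28 = 2 days after the event. Exact binomial intervals for 6 or fewer participants would show only how little is known of the event rate; they do not bear on whether the rule is adequate.

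**Conclusion.** The point holds in conditional form. If no other participant has already had a related Grade 3+ toxicity or the same DLT, a first related Grade 4 or 5 event in Part 2 leads to no ad hoc SMC review under 14.9 and no hold on other participants under 4.4. Separately, 14.9 states no hold on the infusions of those already enrolled even when its two-participant trigger is met.

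The size is a schedule limit, not a forecast: 0 to 2 infusions due for another participant who has already started, with monthly taken as about 30 days and nobody using discretion to pause. No event rate is assumed. What is missing is prompt SMC review and a defined pause, not independent oversight as such. This is a design choice that should be tightened because the foreseen harm is severe and the change is small. Confidence is medium, mainly because any SMC charter or SOP was not available.

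**What to change.** Add to 14.9, with a cross-reference in 4.4:

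1. Any single life-threatening or fatal event at least possibly related to MGD014 is sent to the SMC together with the 24-hour report.
2. Enrollment and all further Part 2 infusions are held until the SMC has given its recommendation.
3. The existing two-participant trigger in 14.9 also holds infusions in participants already enrolled.

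This uses the existing committee and the existing reports. The cost is a few lines of text, an occasional ad hoc SMC call, and possibly an infusion outside the ±1 day window in Appendix 1. The amendment should therefore say how a delayed dose is handled and how soon the SMC is expected to respond. If a charter already contains such a rule, a reference to it in 14.9 and 4.4 would be enough.

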- b. If any of the 3 additional participants experiences a DLT (so in total ≥ 2 of the participants experience a DLT within the same dose cohort), no further participants will receive a dose at this dose level, as the maximum tolerated dose (MTD) will have been exceeded. Part 2 will proceed with the MTD (the dose preceding the dose level at which MTD was exceeded). If only 1 participant was enrolled at the prior dose level, an additional 3 participants will be enrolled at the prior dose level for evaluation of the MTD.

[figure not shown]

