4.3 Multi-Dose Cohort Expansion Phase (Part 2)

Part 2 is a multi-dose expansion cohort with repeat administrations of MGD014 at 300 mcg/kg; see Study Part 2 Schema, **Figure 5**. Up to 6 patients will be enrolled in Part 2.

Participants previously enrolled in and having completed Part 1 may be considered for enrollment in Part 2, provided they continue to meet all eligibility criteria, did not experience any DLT in Part 1, and do not have any detectable ADA at the completion of Part 1.

In Part 2, additional optional assessments on the effects of MGD014 on HIV latent infection parameters include measurements of resting cell infection (frequency of persistent infection of resting CD4 T cells) by QVOA, SCA, and T-cell phenotype and functional properties.

Figure 5 Part 2: Dose Expansion Study Schema

(a) Screening, eligibility and optional baseline leukapheresis (b) optional leukapheresis post-treatment for frequency of persistent infection of resting CD4 T cells.

Abbreviations: ADA = anti-drug antibody; ART = antiretroviral therapy; leuk = leukapheresis; PK = pharmacokinetics; QVOA = quantitative viral outgrowth assay.

Step 1 Optional Baseline Leukapheresis: After obtaining the informed consent and confirmation that the participant qualifies for the study, the participant enrolls in the study. If the participant gives consent, an optional baseline leukapheresis is completed. The resting CD4 T cells obtained in the leukapheresis will determine the baseline frequency of resting CD4 T-cell infection. Additionally, baseline measurements at 2 independent, pre-MGD014 time points will determine baseline T-cell function and SCA levels. Note: if the frequency of resting CD4 T cell infection is ≤ 0.3 infected cells per million (IUPM), as measured by QVOA, a further decrease from this low frequency of infection cannot be definitively measured given the QVOA assay threshold and variance [51].

Step 2 Treatment phase: Eligible participants will continue their ART regimen and receive 3 infusions of MGD014 at the dose of 300 mcg/kg. Participants are monitored for 6 hours on site following their first infusion. Participants will be monitored for 4 hours on site following subsequent infusions. Clinical and laboratory parameters for safety, including clinical assessment

of cytokine release, will be assessed after each MGD014 infusion. PK and PD data will be collected, and serial blood draws will be obtained to assess the impact on T cell functional properties.

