9.4 Enrollment and Registration

Step 1 Visit 1 determines eligibility and enrollment at Visit 2. Once the potential participant has been determined to be eligible for enrollment into the study, the participant must be registered with MacroGenics. The following information should be provided during registration:

- Year of birth
- Date of signed informed consent
- Planned date of first administration

Instructions for the registration process are provided in the Study SOP.

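### In Part 2, two different related Grade 3+ toxicities suspend enrollment and trigger SMC review, but no rule holds dosing of participants already enrolled while the SMC deliberates

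*Protocol*

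**What the plan says.** Four provisions of the protocol bear on this. The SAP adds no stopping or holding rule and relies on the protocol for the design.

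- **4.4, group hold in Part 2.** The trigger is two or more participants with one and the same DLT: if that many "participants experience the same DLT, subsequent administration of the study drug to any participant should be held pending review" by the investigator, sponsor and SMC. A DLT is a drug-related AE of Grade 2 or higher, with two narrow exceptions that apply only at Grade 2.
- **14.9, study-wide rule.** There are two triggers: two or more participants with a related toxicity of Grade 3 or higher (not necessarily the same one), or two or more with the same DLT of Grade 2 or higher. On either, "then enrollment into the study will be temporarily suspended and the independent SMC will be asked to review all safety data". The SMC is also to "recommend how the study should proceed with respect to resuming enrollment and continuing study treatment".
- **5.3, individual rule.** Among the events that end a participant's own infusions is "Development of a DLT at any time following MGD014 infusion".
- **4.3 and 9.4, size and timing.** "Up to 6 patients will be enrolled in Part 2", each due three infusions of 300 mcg/kg on Days 0, 14 and 28. "Step 1 Visit 1 determines eligibility and enrollment at Visit 2", which comes before the first infusion on Day 0.

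**The concern.** The first trigger in 14.9 already treats dissimilar severe events as a signal about the drug that needs independent review. The action attached to it is a pause on enrollment, and whether treatment continues is left as an output of the review. Until the SMC answers, no rule covers participants who are enrolled and part-way through dosing, or enrolled and awaiting their first infusion.

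Part 2 is the first repeat dosing in this first-in-human study, at the top dose. Section 4.3 sets no interval between participants, so several may be on treatment together. Section 14.9 sets no deadline for a triggered review, and routine reports to the SMC are monthly. A participant's course runs only from Day 0 to Day 28, so it could finish before the SMC responds. At stake is avoidable exposure of the remaining participants during a review called because of severe toxicity.

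**Working it through.** The documents give no toxicity rate or operating characteristic for either rule, so there is no figure of the plan's to reproduce.

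**Step 1. Apply the rules to two affected Part 2 participants.**

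| Events | 4.4 hold on all dosing | 14.9 enrollment pause and SMC review | 5.3 |
|---|---|---|---|
| Same DLT, Grade 2 | Yes | Yes | Both affected stop |
| Same DLT, Grade 3 or 4 | Yes | Yes | Both affected stop |
| Different DLTs, both Grade 3 or 4 | **No** | Yes | Both affected stop |
| Different DLTs, both Grade 2 | No | No | Both affected stop |

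The gap is the third row. A related Grade 3+ event within the DLT period is always a DLT, because the exceptions in 4.4 apply only to Grade 2.

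**Step 2. Infusions exposed.** Planned: 6 × 3 = 18.

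- Both events after infusion 1: the other four have up to 4 × 2 = 8 infusions left (8/18 = 44%).
- Both events after infusion 2, with the others at the same stage: 4 × 1 = 4.

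For an assumed review time of *d* days, with the four spread evenly over the 28 days between infusions 1 and 3:

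- 7 days: 4 × 7/14 = 2 infusions fall inside the review.
- 14 days: 4 × 14/14 = 4.
- 28 days: two participants with 2 left and two with 1 left, so 2 × 2 + 2 × 1 = 6. It would be 8 if all four were still in their first cycle.

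**Step 3. Chance of the third row.** Assume a per-participant related Grade 3+ rate *p*, one event type per affected participant, and *k* equally likely types. With *m* of six affected,

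P(gap) = Σ (m ≥ 2) C(6,m) p^m (1−p)^(6−m) × k(k−1)…(k−m+1)/k^m.

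- *p* = 5%: the binomial terms for m = 2, 3, 4 are 0.03054, 0.00214 and 0.00008.
  - k = 2: 0.03054 × 0.5 = 0.0153
  - k = 3: 0.03054 × 0.667 + 0.00214 × 0.222 = 0.0208
  - k = 5: 0.03054 × 0.8 + 0.00214 × 0.48 + 0.00008 × 0.192 = 0.0255
- *p* = 10%: the terms are 0.09842, 0.01458 and 0.00122.
  - k = 2: 0.0492
  - k = 3: 0.0689
  - k = 5: 0.0860

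If one type dominates (assumed 80/10/10), two events differ with probability 1 − (0.64 + 0.01 + 0.01) = 0.34, and three all differ with probability 6 × 0.8 × 0.1 × 0.1 = 0.048. The results fall to 0.03054 × 0.34 + 0.00214 × 0.048 = 0.0105 and 0.09842 × 0.34 + 0.01458 × 0.048 = 0.0342.

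**Step 4. How often the wider trigger would be met.** P(2 or more of 6) = 0.033 at *p* = 5% and 0.114 at *p* = 10%.

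**The case against.** The strongest reply is that no one would in practice keep infusing. This is a single-center study, and dosing is under the principal investigator's supervision (6.7). Safety laboratory results must be reviewed before each administration (9.11). One investigator would therefore know of both events and could stop any participant's infusions at discretion (5.3). Related Grade 3+ events "as well as safety concerns will be communicated within 24 hours to MacroGenics and the UNC IRB", and the sponsor may discontinue the study (16.11.2). All of this stands and limits the harm. It is discretion, though, and 4.4 shows that the protocol prescribes a hold where it wants one.

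A second reply is that recurrence of one event is a recognisable sign of drug effect, so tying the automatic hold to it is defensible. That is reasonable for Grade 2 events. It fits less well for Grade 3+, where 14.9 already calls for group review without requiring sameness.

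Third, the main expected toxicity, CRS/IRR, would usually count as the same DLT, and 2.4.3 reports that none had been observed through Cohort 8 of Part 1. This lowers the probability, as the 80/10/10 calculation shows.

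Finally, the wording about continuing study treatment might be read as implying a hold. The only action stated before the review is suspension of enrollment.

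**Conclusion.** The gap is real but narrow. For two or more different related Grade 3+ toxicities in Part 2, the prescribed action does not cover dosing of participants already enrolled, and with all six enrolled it has no protective effect. On the assumed rates and types, the scenario arises in about 1.5–2.5% (rate 5%) or 4.9–8.6% (rate 10%) of trials, and less often if one event type dominates. The infusion counts rest on assumed stagger and review times.

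A reader might infer more than the documents support:

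- **That milder events draw the stronger response.** The dividing line in 4.4 is sameness, not grade. Two identical Grade 3 or 4 DLTs also trigger the hold, and that hold is temporary; the study is discontinued only if toxicity is judged unacceptable.
- **That Part 2 relaxes a Part 1 rule.** In Part 1, after two DLTs of any kind in a cohort, "no further participants will receive a dose at this dose level, as the maximum tolerated dose (MTD) will have been exceeded". That rule defines the MTD in single-dose escalation. It is not a mid-course hold for people under treatment.
- **That the gap is likely, judging by plausible overall DLT rates.** Those rates include pairs of different Grade 2 DLTs, which do not trigger 14.9 and lie outside this point.

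This is a cheap safety improvement, not a flaw that undermines the study.

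**What to change.** In 4.4, widen the Part 2 hold so that study drug is held for all participants when two or more have the same DLT, **or** when two or more have any drug-related toxicity of Grade 3 or higher. In 14.9, state that for Part 2 the hold accompanies the suspension of enrollment and lasts until the SMC has made its recommendation.

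The drafting cost is one sentence in each section. No new review is created, because the same events already go to the SMC. The operating cost is a hold in about 3% or 11% of trials at assumed related Grade 3+ rates of 5% or 10%. Some of those involve two identical DLTs and would be held under 4.4 anyway, so the added holds are the 1.5–2.5% or 4.9–8.6% above. A hold that runs past the 1-day window at Day 14 or Day 28 can delay or lose infusions in up to four participants, as the existing 4.4 hold already can.
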